9.2.1 Screening LP Exception

If a participant has undergone an LP for another study at your site within 90 days prior to the baseline visit, this LP and collected CSF samples may be used in place of the screening LP with prior approval from ADCS Clinical Operations. ADCS approval may be requested by email ([contact])

9.2.2 Re-screens

Unless otherwise approved by the Project Directors, only one re-screen is allowed per participant, should the original screen be a failure. The re-screen should typically occur at least 3 months after the original screen failure. Individuals who fail screening due to ineligible results from the CSF testing may not be re-screened.

9.3 Baseline Visit

Baseline procedures include cognitive assessments, behavioral assessments, Research Satisfaction Survey, safety assessments, and review of concurrent medications and adverse events that occur in clinic.

For a complete list of all visit procedures, refer to the Schedule of Events (Appendix 1).

Following completion of all baseline procedures, subjects who continue to meet all protocol inclusion criteria and no exclusion criteria, should be scheduled for the confinement visit. The person should then be randomized, dispensed study drug and instructed on proper storage and dosing. The subject should be instructed on 1) when to take the first dose of the study drug and 2) the duration of study drug administration (21-23 days at home) based on the scheduled date of the confinement visit.

9.4 Day 14 Telephone Contact

A telephone call will be conducted at 14 ± 4 days from the baseline visit to assess for any changes in status, adverse events, or concomitant medications. Study medication compliance will be discussed and reminders given about the upcoming confinement visit. If there is an insufficient level of drug compliance (less than 80% overall and or less than 80% in the last week), the site must consult with the Project Directors and Medical Monitor regarding timing and conduct of the remaining confinement visit procedures. It is possible that subjects will be discontinued early from the study due to insufficient drug compliance.

9.5 Confinement Visits

Admission for the confinement visit should occur 21-23 days (± 2 days) following the first dose of study medication. A pre-confinement visit will be conducted 1-3 days prior to admission and a

post-confinement phone follow-up will be conducted approximately 24 hours following discharge. The confinement visit is outlined in Appendix 3, Confinement Visit Diagram.

9.5.1 Pre-Confinement Visit

The Pre-Confinement Visit procedures include a physical and neurological examination, cognitive and behavioral assessments, certain safety assessments (including clinical safety labs), and a review of compliance, concurrent medications and adverse events. The clinical safety labs will be sent to a central lab for analysis. For a complete list of all visit procedures, refer to the Schedule of Events (Appendix 1).

If there is an insufficient level of drug compliance, the site must consult with the Project Directors and Medical Monitor regarding timing and conduct of the Confinement Visit procedures. It is possible that subjects will be discontinued early from the study due to insufficient compliance.

9.5.2 Confinement Visit

The confinement visit will last just over 2 days and will consist of four phases: admission, 36-hour sampling, 12-hour observation, and discharge. Subjects will be provided with meals (note: some restrictions are specified below) and sleeping accommodations during this visit. For a complete list of all visit procedures, refer to the Schedule of Events (Appendix 1) and to the Confinement Visit Diagram (Appendix 3).

Phase 1: Admission

Subjects should arrive fasted in the early morning after an overnight fast. Clinical safety labs will be drawn and sent to the local lab for analysis.

Study drug compliance over the preceding days will be assessed. If there is an insufficient level of drug compliance (less than 80% overall and or less than 80% in the last week), the site must consult with the Project Directors and Medical Monitor regarding timing and conduct of the remaining confinement visit procedures. It is possible that subjects will be discontinued early from the study due to insufficient study drug compliance.

Admission visit procedures include conducting a brief Physical and Neurological Exam, collecting vital signs, reviewing and recording adverse events and concurrent medications. Please refer to Appendix 3.1, Confinement Visit Phase 1: Admission Diagram.

Phase 2: 36-Hour Sampling

For an overview of the 36-Hour Sampling time points, please refer to the Confinement Visit Schedule of Events (Appendix 3.2b).

If no medical or compliance concerns are identified during the admission procedures, the subject will move on to the 36-Hour Sampling Phase, which entails the following procedures:

1. Place an intravenous line (for infusion) as well as a second venous line for blood sampling
2. Place the CSF catheter
3. Collect initial samples of blood and CSF

4. Administer assigned study drug (will vary based on blinded treatment assignments) at 0 hours
5. Begin the $^{13}\text{C}_6$ -labeled “heavy” leucine infusion. Subjects will receive an initial bolus of 3 mg/kg over 10 minutes, followed by 8 hours and 50 minutes of continuous intravenous infusion at a rate of 2 mg/kg/hour. The total leucine administration with the bolus is 9 hours
6. Provide a low leucine meal (NOTE: all food provided during the heavy leucine infusion must conform to low leucine dietary guidelines; refer to Appendix 4, Sample Low Leucine Menu and to the Procedures Manual for more details)
7. Continue with the following for 36 hours:
 - a. Collect CSF (6 mL) and blood (10mL) every 2 hours at the following time points: 0, 2, 4, 6, 8, 10, 12, 14, 16, 18, 20, 22, 24, 26, 28, 30, 32, 34 and 36 hours; all collection times should be calculated from the start of the heavy leucine infusion. Samples should be in separate tubes and sent to the ADCS Biomarker Core
NOTE: If unable to obtain a total of 6 mL CSF at any given collection time (e.g., due to participant headache or participant’s CSF production level) please obtain the maximum amount possible and notify ADCS Clinical Operations
 - b. At 0 hours, an additional 1-2 ml CSF (or volume per Local laboratory requirements) should be sent ambient to the local laboratory for protein, glucose, and cell counts
 - c. Perform safety monitoring every 4 hours while the subject is awake. This includes questions about any symptoms in relation to the CSF catheter (including potential adverse events such as leg or back pain, dizziness or headaches) and vital sign monitoring. Participants also should be asked about pain, redness or swelling at the IV site in the arm
 - d. Administer assigned study drug (will vary based on blinded treatment assignments) every 8 hours – at 8, 16, 24, and 32 hours
 - e. Provide low leucine meals and snacks as needed during the duration of the heavy leucine infusion; return to normal diet after completion of the infusion (Refer to Appendix 4, Sample Low Leucine Menu)
 - f. Subjects remain at bedrest throughout the CSF sampling period of 36 hours. They are allowed to use a bedside commode for toileting
8. 36 hours after the start of the heavy leucine infusion, collect the final blood and CSF samples. An extra 9mL of whole blood should be sent to the central lab for the metabolic panel and a CBC/Diff. An extra 2mL of CSF should be sent to the local lab for protein, glucose, and cell counts
9. Remove the blood and LP catheters
10. Perform final safety monitoring, a brief physical and a brief Neurological Exam

If the subject experiences intolerable AE(s) that require early discontinuation of the sampling procedures and removal of the LP catheter, contact the Medical Monitor and Project Directors as soon as possible to discuss the situation. If feasible, the standard 12-hour observation and discharge procedures should be followed to allow for management and follow-up on the adverse events.

Phase 3: 12-Hour Observation

The subject should be observed for at least 2 hours following removal of the LP catheter. Subjects are allowed to be up and out of bed during this period. The Research Satisfaction Survey should also be administered.

Any clinical safety labs from the pre-confinement visit that were clinically high should be repeated and sent to the local laboratory. A blood patch will be administered as required if a subject exhibits signs of a post-spinal tap headache that is not managed with bed rest, oral and intravenous fluids, caffeine, and/or mild analgesics (e.g., Ibuprofen, Naproxen or Tylenol).

Do not continue administration of study drug after completion of the 36-Hour Sampling Phase. All used and unused study drug should be returned to the clinical site for final accountability. Please refer to Appendix 3.3, Confinement Visit Phase 3:12-Hour Observation Diagram.

Phase 4: Discharge

Prior to discharge, vital signs should be recorded and a review of AE(s) and Concurrent Medications should be conducted. Upon determination by the investigator (or qualified designee) that the subject is stable, the participant will be discharged. If a participant experiences an unstable AE, please contact the Medical Monitor and Project Directors for guidance on the appropriate course of action to be taken. Please refer to Appendix 3.4, Confinement Visit Phase 4: Discharge Diagram.

9.5.3 Post-Confinement 24-Hour Phone Follow-up

Approximately 24 hours following discharge from the Confinement Visit the subject or a person designated to speak for them will be contacted by phone to confirm the subject's well-being and to query about any new AEs.

10 EARLY TREATMENT/STUDY DISCONTINUATION

The investigators at each site will make every reasonable effort to maximize subject retention. However, if an investigator removes a subject from treatment or study, or if a subject declines further treatment or study participation, an early discontinuation visit will be completed as soon as possible following discontinuation. The early discontinuation visit will contain the same assessments as the pre-confinement visit. If an in-person visit is not possible, site personnel will complete as much of the early discontinuation visit as possible by telephone.

Subjects who discontinue from the study prior to completing all protocol procedures may be replaced at the discretion of the Coordinating Center, in consultation with the Sponsor.

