2.2 Secondary Aims

Aim 4: To implement a multicenter lumbar CSF catheter study employing standardized methodology and SILK™ technology. The following criteria will be evaluated as outcomes to determine feasibility:

- Enrollment comparisons of research subjects at each of the 3 sites
- Adequacy of sample collections to permit analyses of PK and PD effects of Posiphen
- Subject satisfaction questionnaires
- Comparison of protocol deviations and variances in data between the sites

Aim 5: To assess the PD effects of treatment with Posiphen versus placebo on the levels of the following biomarkers in CSF of subjects with early AD:

- A β 38 and 40
- sAPP α
- sAPP β
- T-tau protein (T)

Aim 6: To assess whether there are short-term cognitive and/or neuropsychiatric effects of Posiphen in subjects with early AD, either positive or negative.

- ADAS-Cog12
- MMSE
- Neuropsychiatric Inventory (NPI)

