11.1.7 Research Satisfaction Survey (RSS)

The Research Satisfaction Survey (RSS) was adapted from the work of Larsen (Larsen 1979) to measures the satisfaction of elderly volunteers in clinical trials to treat or prevent cognitive loss or dementia. The RSS builds on the Client Satisfaction Questionnaire (CSQ-8) which demonstrates a high degree of validity and internal consistency and measured consumer satisfaction with health and human service programs. Higher scores on the CSQ indicate a greater level of satisfaction in service programs¹⁰²; conversely, lower CSQ-8 scores have been associated with higher dropout rates (Lunnen 1998) and missed appointments in treatment settings (Larsen 1983) and in urban Community Mental Health programs (Larsen 1979). Open-ended questions about satisfaction are part of the CSQ, and allow participants to provide feedback about specific operational procedures of a particular service program (Larsen 1979). The RSS is similarly designed with a 7- item survey and may include additional items to inquire about the specific aspects of a given trial. Four items are designed to be answered with a modified Likert scale and can be used to create a summary score with a range of 4-16, which can be analyzed with parametric statistics; three items provide for open ended responses about the intervention, the assessments and the frequency of visits and may be used to understand retention rates.

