5.2 Secondary Aims

5.2.1 Aim 1

To implement a multicenter lumbar CSF catheter study employing standardized methodology and SILK™ technology. The following criteria will be evaluated as outcomes to determine feasibility:

Enrollment comparisons of research subjects at each of the 5 sites. Screen failure rates will be evaluated by cause, by number and by site. Demographics will be described across sites. There will be comparison of protocol deviations and sampling results between the sites. Adequacy of sample collections to permit analyses of PK and PD effects of Posiphen during the SILK will be tabulated. Description of the adequacy of SILK sampling, Pk and PD during the confinement visits will be undertaken with comparisons across sites.

Research Satisfaction Questionnaires: Descriptive ratings of participants in response to the research study will be undertaken across visits including baseline and post-confinement when this questionnaire was administered. The responses on the survey will be grouped and compared to address the experience across the trial with characterization of the most frequent terms. Cross tabulations and shift tables will be used to address the response to the SILK procedure through its categorical variables and its influence on participant satisfaction. We will explore whether there is any indication of an effect of treatment on these participant profiles.

5.2.2 Aim 2

To assess the PD effects of treatment with Posiphen versus placebo on the levels of the following biomarkers in CSF of subjects with early AD: Ab 38 and 40, sAPPa, sAPPb, total tau protein.

Mean changes in these biomarkers will be compared across treatment arms between baseline and day 21 time 0 prior to the leucine infusion pooling all participants treated with Posiphen vs placebo across cohorts. Linear regression modelling will allow the comparison of mean change scores in the analytes between the active and placebo groups while adjusting for covariates including age, gender, MMSE at baseline, and Apo-e status as well as armcode and dose cohort and cohort-by-armcode interaction.

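### Participants who stop before confinement give no post-baseline Research Satisfaction Survey, so this Aim 4 feasibility outcome describes only those who reach the catheter stay

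*Protocol*

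**What the plan says.** Protocol Section 2.2 lists "Subject satisfaction questionnaires" among the four criteria by which Aim 4 judges feasibility.

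The survey has two scheduled time points:
- **Baseline.** Section 9.3: "Baseline procedures include cognitive assessments, behavioral assessments, Research Satisfaction Survey, safety assessments". Randomization and dispensing follow once the baseline procedures are complete.
- **12-Hour Observation**, after the lumbar catheter is out. Section 9.5.2, Phase 3: "The Research Satisfaction Survey should also be administered".

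The survey row of Appendix 1 marks these two columns and no others. For participants who leave early, Section 10 says: "The early discontinuation visit will contain the same assessments as the pre-confinement visit". Footnote e of Appendix 1 repeats this.

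Section 11.1.7 ties the instrument to retention. It reports that "lower CSQ-8 scores have been associated with higher dropout rates" for the parent questionnaire, and that the open-ended items cover the intervention, the assessments and "the frequency of visits and may be used to understand retention rates".

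SAP Section 5.2.1 plans descriptive ratings at baseline and post-confinement, and: "Cross tabulations and shift tables will be used to address the response to the SILK procedure". It also intends to describe participants' experience over the trial as a whole and to explore whether treatment affects it.

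**The concern.** The early discontinuation visit inherits its content from a visit without the survey. The participants with most to say about why someone leaves this trial are thus asked for their view only before the first dose.

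Three features make this matter:
- Protocol Section 6.2 expects any dropouts to occur before the SILK procedure, which is the period with no survey.
- The missingness can depend on treatment. Section 6.3 discontinues and replaces participants who do not tolerate study drug at home, while the SAP looks for a treatment effect on satisfaction. That comparison would be made only among people who tolerated their assignment long enough to be admitted.
- A participant who withdraws at home to avoid the catheter is direct evidence on the feasibility of a multicenter catheter study, yet would leave no rating after baseline.

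At stake is what the trial can say about acceptability under Aim 4. The primary aims are not affected.

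**Working it through.** **Step 1. Where the survey is given, by participant group.**

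| Group | Baseline | After baseline | Source |
|---|---|---|---|
| Completes confinement | Yes | Yes, 12-Hour Observation | Protocol 9.3, 9.5.2, Appendices 1 and 3.3 |
| Catheter removed early for an intolerable event | Yes | Yes, if the observation phase is feasible | Protocol 9.5.2, end of Phase 2 |
| Stops before confinement | Yes | None | Protocol 9.5.1, 10, Appendix 1 footnote e |

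The 24-hour call (Protocol 9.5.3) asks about well-being and new adverse events and carries no survey. I read the SAP's post-confinement time point as the 12-Hour Observation, since that is the only later survey in the protocol.

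**Step 2. What the SAP does with a missing value.** Section 5.2.1 gives no rule. A baseline-to-post shift table drops participants without a post value unless the plan says otherwise.

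**Step 3. Possible size.** The documents state no satisfaction score, dropout count or score gap, so there is no figure to reproduce. What follows is illustrative.

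Inputs:
- 24 completers, because dropouts are replaced (Protocol 6.2).
- A summary score of 4 to 16 (Protocol 11.1.7).
- k dropouts before confinement, assumed 0 to 6.
- Gap g = completer mean minus dropout mean, assumed -4 to +4 points.

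The dropout share is d = k/(24 + k). The all-participant mean is (1 - d) × completer mean + d × dropout mean. The completers-only mean therefore exceeds it by d × g.

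| k | d | g = -4 | g = 0 | g = +2 | g = +4 |
|---|---|---|---|---|---|
| 0 | 0 | 0 | 0 | 0 | 0 |
| 1 | 1/25 = 0.040 | -0.16 | 0 | +0.08 | +0.16 |
| 3 | 3/27 = 0.111 | -0.44 | 0 | +0.22 | +0.44 |
| 6 | 6/30 = 0.200 | -0.80 | 0 | +0.40 | +0.80 |

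The largest gap the scale allows, 12 points, gives 0.200 × 12 = +2.4 with six dropouts.

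The SAP does not commit to a mean of this score; it plans descriptive ratings, cross tabulations and shift tables. The grid shows the order of magnitude only.

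**The case against.** The strongest defence is that the SAP aims its shift tables at the SILK procedure, and someone who stopped at home never had the catheter and cannot rate it. That stands for the shift table, which should stay limited to those who underwent the procedure. It does not answer the wider aim of describing experience over the trial. Early stoppers have had screening, normally including a lumbar puncture, and may have had weeks of home dosing, all of which the open-ended items can cover.

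It is also fair that satisfaction is one descriptive criterion of a secondary aim with no decision threshold, and that many of the withdrawal reasons in Protocol 10.1 need not reflect dissatisfaction. This limits the importance of the point without removing the gap.

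A reader might infer more than the documents support:
- **That early stoppers are never surveyed, so dropout cannot be studied.** Every randomized participant should have a baseline survey, and baseline scores of later discontinuers can be compared with those of completers. Only the post-baseline rating is missing.
- **That reported satisfaction is biased upward.** Section 11.1.7 makes that direction plausible for dropout, but its evidence is background on a parent instrument in other settings. The sign is not established here.
- **That only those who finish sampling are asked.** Early catheter removal still leads to the observation phase where feasible.
- **That asking soon after catheter removal inflates ratings by missing later headache.** Section 9.5.2 says "The subject should be observed for at least 2 hours following removal of the LP catheter". That is a minimum stay, and nothing ties the survey to hour 2. Protocol 5.3 puts headache needing a blood patch at about 10%, or 24 × 0.10 = 2.4 expected cases, but gives no onset times. Fresh discomfort after 36 hours of bedrest could equally lower scores.

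**Conclusion.** The gap is real and follows directly from the schedule: anyone who stops before confinement has no post-baseline rating for a listed Aim 4 criterion, and the SAP is silent on how to handle it. Trial-level satisfaction, and any treatment comparison of it, will describe those who reached confinement and may be overstated.

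The documents do not determine the sign or size of any bias. The -0.80 to +0.80 range rests wholly on the assumed dropout counts and gaps, and the effect vanishes if nobody stops early or if stoppers and completers would score alike. This is a cheap improvement to what the trial collects, and does not call the Aim 4 plan as a whole into question.

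**What to change.** 1. **Protocol Section 10 and Appendix 1 footnote e:** add the survey to the early discontinuation visit. Section 10 already allows that visit to be completed by telephone as far as possible, so no new contact is needed.
2. **Protocol Section 9.5.2:** state that anyone whose catheter is removed early is also given the survey.
3. **SAP Section 5.2.1:** keep the SILK-response shift table for participants who underwent the procedure. Show discontinuers' survey results separately, and report the number of missing post-baseline surveys with reasons.

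The cost is one schedule entry, a 7-item form and a few minutes of extra contact. Telephone answers may differ from in-clinic ones, so mode should be recorded.

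Repeating the survey at the 24-hour call is at most an optional extra measurement. It should not replace the in-clinic post value: Protocol 9.5.3 lets a designated person answer that call, and later recall is a weak basis in participants selected for cognitive impairment. If the repeat is used, record who responded.

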10.1 Reasons for Early Discontinuation

Participants may withdraw from the study at any time as stated in the informed consent document given to the participant at the screening visit. Participants may also be discontinued from treatment/study for reasons such as the following:

- Adverse experience: The participant has experienced an adverse event that, in the opinion of the investigator, requires early termination. This may include abnormal laboratory values.

- Death.
- Safety risk: Any participant who becomes a safety risk to themselves during the trial will be withdrawn.
- Protocol violation: The participant fails to meet protocol entry criteria or does not adhere to protocol requirements.
- Non-compliance: The participant is non-compliant with completion of study-related evaluations and/ or intake of study drugs.
- In the investigator's judgment, it is in the participant's best interest to discontinue participation in the study.
- Development of suicidal or homicidal ideation requiring hospitalization or confinement.
- Participant has need for a medication prohibited by the protocol.
- Consent is withdrawn. The participant wishes to withdraw from the study, or the legally authorized representative wishes that the participant be withdrawn.
- The study is terminated by the Sponsor/Coordinating Center, alone or at the recommendation of the Data Safety Monitoring Board.
- Lost to follow up. Participant could not be recalled back to conduct follow up visits.
- Loss of informed study partner. The participant no longer has a responsible study partner to oversee participant visits and administration of study drug.
- Coordinating Center (ADCS) request. The Coordinating Center determines it is in the participant's best interest to discontinue participation from the treatment and or study.

